9.5.1.1 Supportive Analysis

A supportive analysis will be performed on the primary estimand using a logistic regression analysis model with treatment group and continuous covariates of age at baseline and number of co-morbidities at baseline included in the model as covariates. Parameter estimates and the corresponding 95% CIs will be provided.

9.5.1.2 Sensitivity Analysis

Alternative methods for handling of intercurrent events will include the following:

- Participants who withdraw consent and have missing disease progression data: The “Composite” strategy will be used. Participants will be considered as having disease progression.
- Participants who withdraw consent and have missing disease progression data: Participants randomized to Placebo will use the “While on Treatment” strategy for this event as described for the primary estimand and participants randomized to INB03 will use the “Composite” strategy.

A tipping point analysis allowing the handling of missing data in the two study arms to vary independently to determine thresholds where there is no longer evidence of a difference in the primary endpoint will be conducted.

Additional sensitivity analyses may be defined in the SAP.

9.5.1.3 Supplementary Analysis

Supplemental analyses will be performed on different populations as defined for the primary estimand ([Section 9.5.1](#)). The estimation methods and estimator of the supplemental analysis estimands are the same as the primary estimand and the statistical analysis methods as described in [Section 9.5.1](#) will be conducted on each supplemental analysis estimand.

- Population: Participants in the ITT population.
 - Intercurrent event: Participants who are randomized who do not receive study treatment – The “Treatment Policy” strategy will be used for these events. Participants will be assessed for the estimator as if they received study drug.
 - Further intercurrent events as defined for the primary estimand will be followed for this sensitivity analysis.
- Population: Participants in the PPS population.

Additional analyses may be described in the SAP.

9.5.2 Secondary Endpoints

Descriptive statistics will be provided for each secondary endpoint and reported by treatment group. Absolute values and changes in inflammatory markers as well as the WHO Ordinal Scale for Clinical Improvement collected each day in hospital will be presented by day and treatment group. Length of stay in index hospital will also be descriptively summarized. The number and percent of participants with the following will be summarized by treatment group:

- Have a 1 point, 2 point etc. increase/decrease in WHO Ordinal Scale
- All-cause mortality at any time within Day 28 visit
- Transfer to ICU level care within Day 28 visit
- Have a new onset of neurological disease within Day 28 visit
- Have evidence of new CHF or new MI requiring medical intervention within Day 28 visit
- Have new onset of embolus or thrombus within Day 28 visit
- Develop need for renal replacement therapy within Day 28 visit

Graphical presentation of endpoint data may be presented and will be described in the SAP.

The secondary estimand population for all secondary endpoints will be estimated based on the mITT population and includes randomized participants who have been diagnosed with COVID-19, have at least one co-morbidity, are admitted to the hospital and have pulmonary complications due to COVID-19 who receive any amount of study drug. To estimate this estimand, all post-randomization data up until Day 28 of the study will be used in the evaluation of each secondary endpoint. Specific handling of intercurrent events for each secondary estimand will be defined in the SAP.

The statistical analyses for secondary estimators with binary outcomes will be performed using CMH tests similar to the primary estimator. In addition, logistic regression analyses as described for the primary efficacy estimator may be performed. Treatment arm will be included in the model as well as age and number of co-morbidities at baseline as covariates. Parameter estimates, odds ratio and the corresponding 2-sided 95% CIs will be provided.

The statistical analysis model for secondary estimators with continuous outcomes will use an analysis of covariance (ANCOVA) or mixed model-repeated measures (MMRM), when assessments are repeated over time, with treatment and age and number of co-morbidities at baseline included as covariates. For MMRM analyses, visit will also be included in the model. The baseline value for change from baseline endpoints will also be included as a variable in the model. Least-square means will be provided for the treatment differences (INB03+SOC vs Placebo + SOC) as well as the corresponding 95% CIs.

9.5.3 Subgroup Analyses

Subgroups may be explored; details will be included in the SAP.

9.5.4 Safety Endpoints

Current standard of care includes assessing vital signs daily and on an as needed basis, clinical laboratory blood collection and ECG assessments. At time of index hospital discharge, laboratory, vital signs and other safety measures as defined on the Schedule of Assessments (Table 3) will be collected. Non-disease related adverse events will be collected until Day 70.

All safety summaries will be provided for the safety set.

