Immunosuppressive treatments to manage acute respiratory distress (ARDS) in COVID-19 patients can have grave consequences as was observed with increased death following corticosteroid treatment (Shang *et al.* 2020). Current treatment strategies such as anti-IL-6 therapies are also immunosuppressive which could impair the ability of the immune system to clear the viral infection or increase the risk of secondary infection. Notably, secondary bacterial infection was observed in more than half of deceased COVID-19 patients (Zhou *et al.* 2020). Viral shedding has been reported for up to eight days after symptoms disappear in more than half of patients and even longer in the more patients with severe disease (Chang *et al.* 2020). Whether or not immunosuppressive therapies extend viral shedding is unknown although patients with severe disease are more likely to receive immunosuppressive treatment.

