7.1.9 Adverse Events

7.1.9.1 Definition of Adverse Events

An AE is defined as any untoward medical occurrence in a clinical study participant administered a medicinal product which does not necessarily have a causal relationship with this treatment. An AE can therefore be any unfavourable and unintended sign (including an abnormal laboratory finding), symptom, or disease temporally associated with the use of a medicinal (investigational) product, whether or not it is related to the medicinal (investigational) product. This includes an exacerbation of pre-existing conditions or events, intercurrent illnesses, drug interaction or the significant worsening of the indication under investigation that is not recorded elsewhere in the CRF under specific efficacy assessments. Anticipated fluctuations of pre-existing conditions, including the disease under study that do not represent a clinically significant exacerbation or worsening need not be considered AEs.

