7.1.9.5 Recording of Adverse Events

Adverse Events will be recorded and reported from the study enrolment until Study Day 70 for all participants who are randomized. Refer to [Section 7.1.9.1](#) for definition of AEs.

When an AE/SAE occurs, it is the responsibility of the investigator to review all documentation (eg, hospital progress notes, laboratory, and diagnostic reports) relative to the event. The investigator will then record all relevant information regarding an AE/SAE in to the CRF. All

CONFIDENTIAL

details of any treatments initiated due to the AE should also be recorded in the participants' notes and the CRF.

Each AE will be documented in the participant's CRF. If an AE changes in frequency or intensity during a study, a new entry of the event must be made in the CRF.

The investigator will attempt to establish a diagnosis of the event based on signs, symptoms, and/or other clinical information. In the absence of a diagnosis, the individual signs/symptoms should be documented.

All AEs occurring during the study must be documented on the relevant CRF pages. The following data should be documented for each AE:

- Description of the symptom event;
- Classification of 'serious' or 'not serious';
- Severity - graded according to the CTCAE v5.0;
- Date of first occurrence and date of resolution (if applicable);
- Action taken;
- Causal relationship;
- Outcome of event (unknown, recovered, not yet recovered, recovered with sequelae, death) [with date and cause reported].

After the initial AE or SAE report, the investigator is required to proactively follow each participant and provide further information to the sponsor on the participant's condition.

All AEs are required to be assessed by a medical practitioner. All AEs or SAEs documented at a previous visit/contact that are designated as ongoing, will be reviewed at subsequent visits/contacts. All AEs or SAEs assessed as related to IP will be followed until Study Day 70. The investigator will ensure that follow-up includes any supplemental investigations as may be indicated to elucidate the nature and/or causality of the AE or SAE.

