9.5.4.1 Adverse Events

Non-disease related AEs will be coded using the MedDRA classification system. Relationship to study drug will be assessed by the investigator and reported on the CRF. Reported AEs, SAEs and related AEs will be summarized by treatment arm and overall and by system organ class (SOC) and by preferred term.

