
 To evaluate if length of hospital-stay in participants with pulmonary complications from COVID-19 infection decreases when treated with INB03 	
 Length of hospital stay defined as the number of days in hospital from time of randomization to time of discharge or death, whichever occurs first

 To assess the effect INB03 has on inflammatory markers in participants with pulmonary complications from COVID-19 infection 	
 Change from baseline in inflammation markers over time
Safety	

 To evaluate the safety and tolerability of INB03 when given to participants with pulmonary complications from COVID-19 infection 	
 Incidence of adverse events and serious adverse events not due to underlying disease Incidence of abnormal findings in clinical safety laboratory parameters, vital signs, and ECGs

Exploratory	
Efficacy	

To qualitatively and quantitatively evaluate the presence and nature of residual (post-Study Day 40) complaints of fatigue, malaise, affective symptoms, inflammatory cognitive dysfunction syndrome and associated functional limitations	
Percentage of participants who report Long COVID symptomsTotal score on the Patient Health Questionnaire-9 (PHQ-9)Total and subscale scores on Long COVID Questionnaire (LCQ)Total and subscale scores on Long COVID Informant Questionnaire (LCIQ)

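### The safety endpoint and Protocol 9.5.4 exclude adverse events due to COVID-19, which contradicts the rules that record and tabulate all adverse events; the exclusion is undefined and infection is the harm most exposed to it

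*Protocol*

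**What the plan says.** Two sets of statements stand side by side.

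Restrictive:
- The safety endpoint in SAP 2 is "Incidence of adverse events and serious adverse events not due to underlying disease". The Protocol synopsis and Protocol 4.2.3 give the same endpoint.
- On collection, Protocol 9.5.4 says "Non-disease related adverse events will be collected until Day 70".
- On coding, Protocol 9.5.4.1 says "Non-disease related AEs will be coded using the MedDRA classification system".

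Unrestricted:
- Protocol 7.1.9.5: "Adverse Events will be recorded and reported from the study enrolment until Study Day 70 for all participants who are randomized", and again "All AEs occurring during the study must be documented on the relevant CRF pages".
- Protocol 7.1.9.1 counts any untoward occurrence, including intercurrent illness. It also counts "the significant worsening of the indication under investigation that is not recorded elsewhere in the CRF under specific efficacy assessments". Its only other exemption is "Anticipated fluctuations of pre-existing conditions, including the disease under study that do not represent a clinically significant exacerbation or worsening need not be considered AEs".
- Protocol 7.1.9.6 requires every SAE to be reported, whether or not it is related to the product. Footnote 13 of the Schedule of Assessments records AEs to Day 70 for everyone randomised.
- SAP 6.3.1 defines treatment emergence by timing, worsening and seriousness. It tabulates treatment-emergent events, Grade 3 or higher events and SAEs by arm, and lists every reported AE.

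**The concern.** The placebo arm already separates drug effect from disease. Screening events by presumed cause before they are collected or coded gains nothing, and it can remove the events on which the arms might differ.

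The risk is greatest where a suspected harm resembles the disease. Protocol 2.2 says available TNF antagonists raise the risk of infection. Protocol 2.4 bases potential risks partly on events seen with other TNF antagonists, and Protocol 2.1.2 rests the rationale on INB03 leaving the response to infection intact. Yet Protocol 2.1.1 notes that "secondary bacterial infection was observed in more than half of deceased COVID-19 patients". An investigator could plausibly put a late pneumonia or sepsis down to COVID-19 and, following 9.5.4, not record it. What is at stake is how completely the safety and tolerability objective is answered, above all for infection.

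**Working it through.** The documents state no figure to reproduce. The check is a comparison of passages, followed by an illustration of size.

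**1. Can the restriction be applied as written?** Not reproducibly. Neither document gives a definition, criteria or adjudication for an event due to the underlying disease. The data items listed for each AE in Protocol 7.1.9.5 include no disease attribution. The causality scale in 7.1.9.4 covers relationship to study product only and cannot stand in for it: Not Related does not mean due to COVID-19, and Possibly Related includes events that the participant's clinical state could have caused.

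**2. Does SAP 6.3.1 repair the conflict?** Only in part. It tabulates what was recorded. If sites followed 7.1.9.5, the tables are complete, but the SAP then has no rule for deriving its own Section 2 endpoint. If some sites followed 9.5.4, the missing events cannot be seen in the data.

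**3. Which events have another route into a by-arm comparison?** Protocol 7.2.1 separately collects ventilation, death, ICU-level transfer, MI or CHF, renal replacement, neurologic events and thrombosis or embolism, to Day 40. Infection is not on that list, and neither document plans an infection summary. SAP 6.2 and 6.2.2.2 compare these complications only up to Day 28. After that the picture is:
- Days 29 to 40: a complication treated as disease worsening and recorded on the efficacy pages need not be an AE under 7.1.9.1, and could appear in listings only.
- Days 41 to 70: AE capture is the only route.

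**4. Illustration of size.** All rates are assumed. Let *m* be the share of infections attributed to COVID-19 and left out, equal in both arms.

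Observed rate = true rate × (1 − *m*).

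Power (two-sided 0.05) = Φ{[|p₁ − p₀|√n − 1.96√(2p̄(1 − p̄))] / √[p₀(1 − p₀) + p₁(1 − p₁)]}, where p̄ is the mean of p₀ and p₁.

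The 173 per arm is the planned treated number (Protocol 9.1). The 38 per arm is about half of the 77 dosed (SAP 6.2.4); an even split is assumed.

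Worked for 10% against 20%, n = 173:
- *m* = 0: (0.10 × √173 − 1.96 × √0.255) / √0.25 = (1.315 − 0.990) / 0.5 = 0.651, so power is 74%.
- *m* = 0.5 (5% against 10%): (0.658 − 0.730) / 0.371 = −0.195, so power is 42%.

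| *m* | Observed rates | Difference (points) | Ratio | Power, 173 per arm | Power, 38 per arm |
|---|---|---|---|---|---|
| 0% | 10% v 20% | 10.0 | 2 | 74% | 23% |
| 25% | 7.5% v 15% | 7.5 | 2 | 60% | 18% |
| 50% | 5% v 10% | 5.0 | 2 | 42% | 13% |
| 75% | 2.5% v 5% | 2.5 | 2 | 23% | 8% |

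For true rates of 5% and 15%, power at 173 per arm is 88%, 76%, 57% and 32% for the same values of *m*.

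**The case against.** The best defence is that the sections sites work from carry no restriction. Protocol 7.1.9 and the Schedule of Assessments ask for all AEs and SAEs, whereas 9.5.4 sits in the statistics chapter. A new secondary infection is an intercurrent illness under 7.1.9.1, so it is reportable, and it is an SAE if it meets 7.1.9.2. Most other harms that resemble COVID-19 are compared by arm to Day 28, and infection leading to ventilation or death by then counts in the primary endpoint. Under Protocol 5.5 the DMC receives unblinded SAEs within 48 hours of their report to the sponsor. With about 38 per arm, power is only 23% in the illustration even with complete capture, so sample size limits the safety comparison more than wording does.

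All of that stands, and it rules out three stronger readings that a reader might take from 9.5.4:
- That the plan keeps only events unrelated to the disease. The conduct sections and SAP 6.3.1 say otherwise.
- That the safety objective cannot be answered. The arms are randomised and blinded, and unrestricted treatment-emergent, serious and fatal event summaries are planned.
- That a drug which raised infections would be expected to show equal or lower rates. With equal attribution the ratio is unchanged. For 10% and 20% to look alike, 0.20 × (1 − m₁) must equal 0.10 × (1 − m₀), so INB03 infections would have to be kept at half the placebo proportion, for example m₁ = 75% with m₀ = 50%. Nothing in the documents suggests such an imbalance under blinding.

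The defence does not remove the conflict. The endpoint itself carries the restriction in both documents, nobody is told how to apply it, and infection has no second route of capture.

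**Conclusion.** The documents contradict each other on which adverse events are collected, coded and counted in the safety endpoint, and the restrictive version is undefined. Applied as written, it could omit disease-attributed events, chiefly secondary infections and events after Day 28. If attribution is equal between the blinded arms, the result is a smaller absolute difference and lower power with the ratio unchanged. The actual size is unknown: the documents give neither an infection rate nor an attribution rate, and they do not show which rule sites followed. The illustration rests on assumed rates and on equal attribution. The passages should be reconciled before final lock, because doing so is cheap and removes an avoidable source of bias.

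**What to change.** Reconcile the passages in favour of the unrestricted rule:
- Delete the disease qualifier from the safety endpoint (Protocol synopsis, Protocol 4.2.3, SAP 2) and from the collection and coding sentences in Protocol 9.5.4 and 9.5.4.1.
- Code all treatment-emergent AEs and SAEs and summarise them by arm regardless of attribution, as SAP 6.3.1 already plans. Show any disease-attributed split only as a descriptive addition.
- Optionally, add a by-arm summary of infections other than COVID-19 from the coded AE data.

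Enrolment ended on 15 June 2021, so the practical vehicle is the SAP, which Section 1 allows to be amended before final lock. The study report should state which recording rule sites followed, since a SAP change cannot restore events that were never recorded. The change also leaves the 7.1.9.1 exemption in place for worsening recorded on the efficacy pages.

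The cost is wording and longer AE tables with more background disease events in both arms. No visits or procedures are added, because Protocol 7.1.9.5 already asks for all AEs.

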9.5.4.1 Adverse Events

Non-disease related AEs will be coded using the MedDRA classification system. Relationship to study drug will be assessed by the investigator and reported on the CRF. Reported AEs, SAEs and related AEs will be summarized by treatment arm and overall and by system organ class (SOC) and by preferred term.

9.5.4.2 Vital Signs, Electrocardiogram and Laboratory Assessments

Vital signs and laboratory tests will be summarized as absolute values and change from baseline by treatment arm. Participants with fever ($\geq 38^{\circ}\text{C}$) and days with fever will be tabulated. Baseline is defined as the latest value in the database prior to randomization. Listings of abnormal laboratory parameter results will be provided.

Electrocardiogram data collected throughout the study period will be provided in data listings.

9.6 Other Analyses

9.6.1 Demographics and Baseline Characteristics

Participant demographics and baseline co-morbidities will be collected at screening and summarized by treatment arm and overall.

The date of COVID-19 confirmed case will also be collected. Further data to be collected includes date and time of admission to hospital and date participant first knew they had a fever.

9.6.2 Prior and Concomitant Medications

Prior medication collection will be limited to medications required for review of entry criteria. Medications participant is currently taking as well as new medications prescribed while on study will be collected in the CRF. All medications will be coded according to the World Health Organization (WHO) Drug Dictionary and provided in patient listings.

9.6.3 SaO₂

Absolute values and changes at each timepoint of collection will be reported. Baseline is defined as the latest value in the database prior to randomization. All data will be included in patient listings.

9.6.4 Other Efficacy Assessments

Chest imaging may be performed throughout the study as deemed necessary by the investigator to assess COVID-19 disease. Imaging details will be provided in a listing.

Participants are to complete the LCQ and the PHQ-9 on Day 40-50. The percentage of participants who complete the LCQ and PHQ-9 will be reported. The total and subscale scores from the LCQ and total score from the PHQ-9 will be summarized descriptively and reported by treatment group. Similarly, the total and subscale scores from the LCIQ will be summarized.

9.7 Analysis and Reporting

9.7.1 Interim Analyses

An interim analysis will be performed when approximately 70 participants in the mITT population have completed the Study Day 28 assessment or who have an intercurrent event within 28 days on study (withdrawal or lost to follow-up). Imputation of missing data will be performed as described in [Section 9.5.1](#).

Efficacy data, including the primary endpoint and cumulative safety data will be reviewed at the time of the interim analysis by the DMC.

A non-binding one-way futility analysis will be performed. The futility boundaries were derived using custom Z-statistic. The Z-statistic chosen as the boundary is considered clinically relevant and has a high probability of success at the final analysis with conditional power of at least 81.5%. At the time of the interim analysis, the Z-statistic boundary was chosen based on a 7.5% treatment difference corresponding to a placebo event rate of 20% and INB03 event rate of 12.5%. The futility boundary will be set at $Z < -0.8505$ (one-sided test). Should the result of the primary endpoint analysis Z-statistic be greater than -0.8505 (one-sided p-value ≥ 0.1975), the futility boundary will be considered crossed, and futility assumed. At the time of interim analysis, the boundary may be recalculated based on true number of participants with evaluable data included in the interim analysis population.

In order to maintain the study blind, an independent unblinded statistical team not involved in the conduct of the study will perform the analyses and present the results to the DMC during a closed meeting where only the DMC members and the unblinded statistician attend.

A preliminary analysis of the primary efficacy data will be performed prior to the final database lock. The primary efficacy endpoint will be analyzed and a limited number of individuals who are not involved in the study conduct or review of day-to-day activities of the study will be informed on the unblinded efficacy results in order to plan further development and inform on other corporate objectives. The DMC will also review unblinded safety and the primary efficacy data and recommend to the sponsor their unbiased opinion concerning safety and efficacy of INB03 in an acute COVID population.

The futility analysis is non-binding and the DMC will make a recommendation based on review of primary efficacy and safety data. The DMC will recommend the trial continue as planned or be terminated due to futility or safety concerns. There will be no early termination due to positive efficacy signals.

The decision to terminate the trial will be at the sole discretion of the sponsor.

